#### **4.3.1.4 Time to Return to Normal Health and Activity**

“Normal health and activity” is identified by a “yes” response to the following question on the CARIFS: “Since the last assessment has the patient been able to return to day care/school, or resume his or her normal daily activity in the same way as performed prior to developing the flu?”.

Time to return to normal health and activity will be summarized using descriptive statistics by treatment, as well as Kaplan-Meier plots.

Patients who do not return to normal health and activity will be censored at the last observation timepoint.

Patients in FASi will be removed from this analysis if a 'Yes' response to this item is reported at baseline.

#### **4.3.1.5 Frequency of Influenza-Related Complications**

Influenza-related complications include death, hospitalization, radiologically-confirmed pneumonia, bronchitis, sinusitis, otitis media, encephalitis/encephalopathy, febrile seizures and myositis, as recorded by question “If this event is one of the following influenza-related complications, select from the list” on the AE CRF form.

The number of influenza-related complications, as well as the number and percentage of patients with these complications, after treatment, will be presented by treatment.

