| 
 To describe the clinical efficacy of baloxavir marboxil compared with oseltamivir in Chinese pediatric participants | 
 Population: All participants aged 1 to < 12 years with influenza symptoms who received at least 1 dose of study treatment who have had a laboratory confirmation of influenza infection (PCR result) from any swab sample collected at baseline or during the study Endpoints: 
 Time to alleviation of influenza signs and symptoms, defined as the length of time taken from the start of treatment to the point at which all of the following criteria are met and remain so for at least 21.5 hours: 
 A score of 0 (no problem) or 1 (minor problem) for cough and nasal symptoms (Items 14 and 15 of the CARIFS, see Section A5–1.1). A "yes" response to the following question on the CARIFS: "Since the last assessment has the subject been able to return to day care/school (if applicable), or resume his or her normal daily activity in the same way as performed prior to developing the flu?" (if possible). Return to afebrile state (tympanic temperature $\leq 37.2^{\circ}\text{C}$). Duration of fever (time to return to afebrile state [tympanic temperature $\leq 37.2^{\circ}\text{C}$] and remaining so for at least 21.5 hours) Duration of symptoms (alleviation of all symptoms as defined by a score of 0 [no problem] or 1 [minor problem] and remaining so for at least 21.5 hours, for all 18 symptoms specified in the CARIFS questionnaire) Time to return to normal health and activity based on the CARIFS questionnaire Frequency of influenza-related complications (death, hospitalization, radiologically confirmed pneumonia, bronchitis, sinusitis, otitis media, encephalitis/encephalopathy, febrile seizures, myositis) Proportion of participants requiring antibiotics for influenza related complications Treatment: 
 Experiment arm: baloxavir marboxil single dose Control arm: oseltamivir 5 days BID Intercurrent events and handling strategies 
 Treatment discontinuation: treatment policy strategy with use of appropriate summary statistics |

Table 3 Primary and Secondary Objectives and Corresponding Estimand (cont.)

| Efficacy (Secondary) Objective | Estimand Definition |
|--|---|

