- Exacerbation of a chronic or intermittent preexisting condition, including either an increase in frequency and/or intensity of the condition
- New condition detected or diagnosed after study treatment administration, even though it may have been present before the start of the study
- Signs, symptoms, or clinical sequelae of a suspected drug–drug interaction
- Signs, symptoms, or clinical sequelae of a suspected overdose of either study treatment or a concomitant medication

Overdose per se will not be reported as an adverse event or serious adverse event unless it is an intentional overdose taken with possible suicidal or self-harming intent. Such overdoses should be reported regardless of sequelae.

- "Lack of efficacy" or "failure of expected pharmacological action" per se will not be reported as an adverse event or serious adverse event. Such instances will be captured in the efficacy assessments. However, the signs, symptoms, and/or clinical sequelae resulting from lack of efficacy will be reported as an adverse event or serious adverse event if they fulfill the definition of an adverse event or serious adverse event.

Appendix 3: Adverse Events: Definitions and Procedures for Recording, Evaluation, Follow-Up, and Reporting

Events NOT Meeting the Definition of Adverse Event

The following events do not meet the definition of adverse event:

- Any clinically significant abnormal laboratory findings or other abnormal safety assessments that are associated with the underlying disease, unless judged by the investigator to be more severe than expected for the participant's condition
- The disease or disorder being studied or expected progression, signs, or symptoms of the disease or disorder being studied, unless more severe than expected for the participant's condition
- Medical or surgical procedure (e.g., endoscopy, appendectomy)
The condition that leads to the procedure is the adverse event.
- Situations in which an untoward medical occurrence did not occur (social and/or convenience admission to a hospital)
- Anticipated day-to-day fluctuations of a preexisting disease or condition present or detected at the start of the study that do not worsen

A3–2 DEFINITION OF SERIOUS ADVERSE EVENT

If an event is not an adverse event per the definition in Section [A3–1](#), it cannot be a serious adverse event even if serious conditions are met (e.g., hospitalization for signs or symptoms of the disease under study, death due to progression of disease).

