The finding of an elevated ALT or AST ($> 3 \times \text{ULN}$) in combination with either an elevated total bilirubin ($> 2 \times \text{ULN}$) or clinical jaundice in the absence of cholestasis or other causes of hyperbilirubinemia is considered to be an indicator of severe liver injury (as defined by Hy's Law). Therefore, investigators must report as an adverse event the occurrence of either of the following:

- Treatment-emergent ALT or AST $> 3 \times \text{ULN}$ in combination with total bilirubin $> 2 \times \text{ULN}$
- Treatment-emergent ALT or AST $> 3 \times \text{ULN}$ in combination with clinical jaundice

The most appropriate diagnosis or (if a diagnosis cannot be established) the abnormal laboratory values should be recorded on the Adverse Event eCRF (see Section [A3-7.1](#)) and reported to the Sponsor immediately (i.e., no more than 24 hours after the investigator becomes aware of the event), either as a serious adverse event or an adverse event of special interest (see Section [A3-5](#)).

A3-7.7 DEATHS

All deaths that occur during the protocol-specified adverse event reporting period (see Section [8.3.1](#)), regardless of relationship to study treatment, must be recorded on the Adverse Event eCRF and immediately reported to the Sponsor (see Section [A3-5](#)). This includes death attributed to progression of influenza.

Death should be considered an outcome and not a distinct event. The event or condition that caused or contributed to the fatal outcome should be recorded as the single medical concept on the Adverse Event eCRF. Generally, only one such event should be reported. If the cause of death is unknown and cannot be ascertained at the time of reporting, **"unexplained death"** should be recorded on the Adverse Event eCRF. If the cause of death later becomes available (e.g., after autopsy), "unexplained death" should be replaced by the established cause of death. The term **"sudden death"** should not be used unless combined with the presumed cause of death (e.g., "sudden cardiac death").

Appendix 3: Adverse Events: Definitions and Procedures for Recording, Evaluation, Follow-Up, and Reporting

If the death is attributed solely to progression of influenza, "influenza progression" should be recorded on the Adverse Event eCRF.

Deaths that occur after the adverse event reporting period should be reported as described in Section [A3-6](#).

A3-7.8 PREEXISTING MEDICAL CONDITIONS

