A preexisting medical condition is one that is present at the screening visit for this study. Such conditions should be recorded on the General Medical History and Baseline Conditions eCRF.

A preexisting medical condition should be recorded as an adverse event only if the frequency, severity, or character of the condition worsens during the study. When recording such events on the Adverse Event eCRF, it is important to convey the concept that the preexisting condition has changed by including applicable descriptors (e.g., "more frequent headaches").

A3-7.9 LACK OF EFFICACY OR WORSENING OF INFLUENZA

Medical occurrences or symptoms of deterioration that are anticipated as part of influenza should not be recorded as adverse events. However, deterioration that is judged by the investigator to have unexpectedly worsened in severity or frequency or changed in nature at any time during the study should be recorded as an adverse event. When recording an unanticipated worsening of influenza on the Adverse Event eCRF, it is important to convey the concept that the condition has changed by including applicable descriptors (e.g., "accelerated worsening of influenza").

A3-7.10 HOSPITALIZATION OR PROLONGED HOSPITALIZATION

Any adverse event that results in hospitalization (i.e., inpatient admission to a hospital) or prolonged hospitalization should be documented and reported as a serious adverse event (per the definition of serious adverse event in Section [A3-2](#)), except as outlined below.

An event that leads to hospitalization under the following circumstances should not be reported as an adverse event or a serious adverse event:

- Hospitalization for respite care
- Hospitalization for a preexisting condition, provided that all of the following criteria are met:
 - The participant was hospitalized for an elective procedure that was planned prior to the study, was scheduled during the study despite the fact that the condition had not worsened, or was scheduled during the study when treatment

Appendix 3: Adverse Events: Definitions and Procedures for Recording, Evaluation, Follow-Up, and Reporting

became necessary because of the expected normal progression of the condition

- The participant has not experienced an adverse event

An event that leads to hospitalization under the following circumstances is not considered to be a serious adverse event, but should be reported as an adverse event instead:

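### Influenza complications are counted only from the adverse event form, whose rules can keep off events judged anticipated and admissions for expected influenza symptoms, so the endpoint is open to under-ascertainment

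*SAP*

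**What the plan says.** **The endpoint.** Protocol Section 3 (Table 3) lists among the secondary efficacy endpoints "Frequency of influenza-related complications (death, hospitalization, radiologically confirmed pneumonia, bronchitis, sinusitis, otitis media, encephalitis/encephalopathy, febrile seizures, myositis". SAP 4.3.1.5 gives the data source: "Influenza-related complications include death, hospitalization, radiologically-confirmed pneumonia, bronchitis, sinusitis, otitis media, encephalitis/encephalopathy, febrile seizures and myositis, as recorded by question". The question, on the AE form, reads "If this event is one of the following influenza-related complications, select from the list". The SAP will report the number of complications, and the number and percentage of patients with them, by treatment.

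**The rules for that form.**
- Protocol A3-1 excludes from the AE definition the studied disease and its "expected progression, signs, or symptoms of the disease or disorder being studied, unless more severe than expected for the participant's condition".
- Protocol A3-7.9 states: "Medical occurrences or symptoms of deterioration that are anticipated as part of influenza should not be recorded as adverse events". It goes on to require recording of "deterioration that is judged by the investigator to have unexpectedly worsened in severity or frequency or changed in nature at any time during the study".
- Protocol A3-2 says of an event that is not an AE under A3-1 that "it cannot be a serious adverse event even if serious conditions are met (e.g., hospitalization for signs or symptoms of the disease under study". The same bracket gives death from disease progression as a second example.
- Protocol A3-7.7 requires all deaths in the reporting period on the AE form, whatever their relationship to treatment, and adds: "This includes death attributed to progression of influenza".

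**The concern.** The complication question refers to an event already entered, so it can be answered only where an AE record exists. The endpoint therefore inherits every exclusion in the AE rules. Those rules are written to keep the studied disease out of the safety data, whereas the endpoint is meant to count consequences of that disease. Neither document tells sites which purpose prevails when a listed complication is also an anticipated part of influenza.

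Hospitalization is a named component. An admission that a site treats as a non-AE would be missing from the complications table and also from the AE and serious AE tables, which serve the primary objective. The study is open-label, so whether an event was expected is judged by someone who knows the treatment. Any omission could differ between arms.

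**Working it through.** **Step 1: is there another source?** None is stated.
- Protocol 8.1 lists only the CARIFS questionnaire as an efficacy assessment.
- The schedule of activities (Table 1) has no row for complications or hospitalizations.
- Protocol 8.9 says medical resource utilization is not assessed.
- A3-1 keeps lack of efficacy off the AE form because the efficacy assessments will capture it. For complications, SAP 4.3.1.5 sends that capture back to the AE form, which is circular.

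**Step 2: the components against the recording rules.**

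| Component | Rule that favours recording | Rule that allows omission | Result |
|---|---|---|---|
| Death | A3-7.7, all deaths including influenza | A3-2 example (progression) | Captured by the specific rule; wording conflicts |
| Hospitalization | A3-1 and A3-7.9 exceptions if worse than expected | A3-2 example (symptoms of the studied disease) | Depends on the site's reading |
| Pneumonia, otitis media, sinusitis, encephalitis/encephalopathy, myositis | A3-1, new condition diagnosed after dosing; A3-3.1, record the diagnosis | A3-7.9 if judged anticipated | Ordinarily recorded |
| Febrile seizures | As above; A3-2 also names convulsions among its medically important events | A3-7.9 if judged anticipated | Probably recorded |
| Bronchitis | A3-1, new condition | A3-7.9; A3-7.2 puts non-severe, non-serious secondary events under their primary cause, here possibly influenza, itself not an AE | Can be read either way |

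**Step 3: does A3-7.10 settle admissions?** It requires an AE that leads to hospitalization to be reported as serious, and its listed exceptions do not include influenza. But it starts from an event that is already an AE. If A3-1 has removed the event, A3-7.10 never applies.

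**Step 4: size.** The documents give no expected complication rate and no share of complications likely to be recorded, so there is no planned figure to reproduce for this endpoint. Planned arms are 67 and 33 (Protocol 9.1.1). One affected child missed is 1/67 = 1.5 or 1/33 = 3.0 percentage points. The analysis uses the FASi, which may be smaller, so each child may weigh slightly more.

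For illustration only, assume a true rate p and a recorded share f. Expected recorded count = n × p × f. Probability of at least one recorded case in the baloxavir arm = 1 − (1 − p × f)^67. With p = 3% and f = 1 this gives 87.0%, and with p = 5% it gives 96.8%, matching the 87% and 97% in Protocol Table 8.

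| Assumed p | Assumed f | Expected, n = 67 | Expected, n = 33 | P(at least 1), n = 67 |
|---|---|---|---|---|
| 5% | 100% | 3.35 | 1.65 | 96.8% |
| 5% | 75% | 2.51 | 1.24 | 92.3% |
| 5% | 50% | 1.68 | 0.83 | 81.7% |
| 5% | 25% | 0.84 | 0.41 | 56.9% |
| 10% | 100% | 6.70 | 3.30 | 99.9% |
| 10% | 50% | 3.35 | 1.65 | 96.8% |

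The counts are small even with complete recording, so one or two omitted children would visibly alter the table. Neither p nor f comes from the documents.

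**The case against.** The strongest reply is that the exclusions are conditional and the exceptions are broad. Events more severe than expected, unexpectedly worsened or changed in nature are recorded. New diagnoses after dosing are AEs, and sequelae of lack of efficacy are reported if they meet the AE definition. Protocol 5.2 excludes children who need inpatient treatment at entry, so a later admission can readily be argued to be more severe than expected. The form itself offers hospitalization and death as options, which suggests they are meant to be entered. The eCRF completion guideline is not among the documents and might already contain the missing instruction.

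Most of this stands. A reader might infer that the protocol bars influenza complications from the AE form, that a child admitted for influenza is never entered, or that the endpoint is under-counted by design. The documents do not support those readings: the exceptions let most listed diagnoses through, A3-7.7 secures deaths, and A3-2 denies serious AE status only to an event already judged not to be an AE.

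What the reply does not do is close the gap for admissions. A site must argue from the entry criterion against A3-2's explicit example, and two sites could reasonably differ.

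There is also a partial backstop. Protocol 6.8 records the reason for each concomitant medication, so a complication treated with antibiotics leaves a trace. But SAP 4.3.1.6 counts antibiotics for any reason, nothing feeds that record into SAP 4.3.1.5, and it does not cover admissions or complications managed without antibiotics.

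**Conclusion.** The point holds as a conflict between stated rules. The sole source of the endpoint is a form from which events judged anticipated as part of influenza are kept off. Under-ascertainment is possible, chiefly for admissions for expected influenza symptoms and for complications such as bronchitis that a site regards as anticipated. Because treatment is known, the omission could differ by arm; nothing in the documents shows that it would.

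The size cannot be derived. The firm figures are 1.5 and 3.0 percentage points per missed child at the planned arm sizes. A reader might infer that a third or more of the control-arm events would be lost. That figure arises only by assuming a 5–10% rate (33 × 0.05 = 1.7 to 33 × 0.10 = 3.3 children) and then assuming that one or two of them are missed; neither assumption has a source in the documents.

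This is one descriptive secondary endpoint with no hypothesis test, so the issue does not threaten the trial's main purpose. It should still be corrected, because following the rules as written can drop true endpoint events. Separately, A3-2 and A3-7.7 contradict each other on deaths from disease progression. A3-7.7 should secure the data, but the two passages must be reconciled.

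**What to change.** State in Protocol A3-7.9 and in the eCRF instructions that every event on the complication list, including any hospitalization after dosing, is recorded and the complication question answered, whether or not the event was anticipated. Either of two routes would work:
- Use the AE form with a flag for anticipated events. AE incidence is part of the primary endpoint, so the SAP should then show the AE tables with and without flagged records.
- Use a separate complications form, which leaves the AE definition and the primary tables untouched.

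Name the chosen source in SAP 4.3.1.5, and align A3-2's example of death from disease progression with A3-7.7.

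The cost is a short protocol clarification, an update to the eCRF instructions, a few more records, and either a filter on the AE tables or one additional form. If the eCRF guideline already contains the instruction, the remaining work is to bring Appendix 3 and the SAP into line with it.

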#### **4.3.1.6 Proportion of participants requiring antibiotics for influenza related complications**

The number and percentage of patients requiring antibiotics for any reason will be presented by treatment group.

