6.8 CONCOMITANT THERAPY

Concomitant therapy consists of any medication (e.g., prescription drugs, over-the-counter drugs, vaccines, herbal or homeopathic remedies, nutritional supplements) used by a participant in addition to protocol-mandated treatment from 2 weeks prior to the initiation of study drug to the study completion/discontinuation visit.

All such medications must be reported to the investigator and recorded on the Concomitant Medications eCRF along with the following information:

- Reason for use
- Dates of administration, including start and end dates
- Dosage information, including dose and frequency

The Medical Monitor may be consulted if there are any questions related to concomitant or prior therapy.

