6.8.4 Prohibited Therapy

The use of the following drugs and over-the-counter drugs will be prohibited from the time of signing the informed consent until completion of study assessments on Day 15 (or until completion of assessments at study withdrawal). The concomitant use of topical skin preparations like a compress is allowed.

- Antipyretics/analgesics other than acetaminophen
- Corticosteroids in oral, injection, or *nasal* formulation

Only systemic (oral, injection, rectal or enema) and nasal formulations will be prohibited. The concomitant use of inhaled corticosteroids is allowed, and any changes in dose and mode of administration should be recorded.

- Immunosuppressive agents
- Antibiotics and antifungals

Unless bacterial or fungal infection is suspected after study drug administration.

- *Other systemic antivirals except for study drugs, including traditional Chinese medicines with antiviral effects*
- Influenza vaccines
- Other investigational drugs

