## 1. INTRODUCTION

The analyses described in this Statistical Analysis Plan (SAP) will supersede those specified in Protocol YV44465 for the purposes of a regulatory filing.

The objective of this study is to evaluate the safety, pharmacokinetics, and efficacy of baloxavir marboxil in Chinese pediatric participants aged 1 to <12 years with influenza symptoms.

There are no changes to the planned analyses described in the protocol.

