**Table 1 Primary and Secondary Objectives and Corresponding Estimand (cont.)**

Efficacy (Secondary) Objective	Estimand Definition

 
To describe the clinical efficacy of baloxavir marboxil compared with oseltamivir in Chinese pediatric participants
 
	
 
Population: All participants aged 1 to <12 years with influenza symptoms who received at least 1 dose of study treatment who have had a laboratory confirmation of influenza infection (PCR result) from any swab sample collected at baseline or during the study
 
Endpoints: 
 
Time to alleviation of influenza signs and symptoms, defined as the length of time taken from the start of treatment to the point at which all of the following criteria are met and remain so for at least 21.5 hours: 
 
A score of 0 (no problem) or 1 (minor problem) for cough and nasal symptoms (Items 14 and 15 of the CARIFS, see Appendix 1.
 
A "yes" response to the following question on the CARIFS: "Since the last assessment has the subject been able to return to day care/school (if applicable), or resume his or her normal daily activity in the same way as performed prior to developing the flu?" (if possible).
 
Return to afebrile state (tympenic temperature <math>\leq 37.2^{\circ}\text{C}</math>).
 
 
 
Duration of fever (time to return to afebrile state [tympenic temperature <math>\leq 37.2^{\circ}\text{C}</math>] and remaining so for at least 21.5 hours)
 
Duration of symptoms (alleviation of all symptoms as defined by a score of 0 [no problem] or 1 [minor problem] and remaining so for at least 21.5 hours, for all 18 symptoms specified in the CARIFS questionnaire)
 
Time to return to normal health and activity based on the CARIFS questionnaire
 
Frequency of influenza-related complications (death, hospitalization, radiologically confirmed pneumonia, bronchitis, sinusitis, otitis media, encephalitis/encephalopathy, febrile seizures, myositis)
 
Proportion of participants requiring antibiotics for influenza related complications
 
 
 
Treatment: 
 
Experiment arm: baloxavir marboxil single dose
 
Control arm: oseltamivir 5 days BID
 
 
 
Intercurrent events and handling strategies 
 
Treatment discontinuation: treatment policy strategy
 
 
 

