### **2.2 SAMPLE SIZE DETERMINATION**

No formal sample-size calculations were performed. Approximately 100 pediatric participants (67 participants in the baloxavir marboxil treatment group and 33 participants in the oseltamivir treatment group) are planned to be enrolled.

The sample size of 67 participants in the baloxavir marboxil treatment group will provide a probability of 87% to detect an adverse event with a 3% incidence rate for at least 1 participant. The given sample size provides a probability of at least 1 participant experiencing an adverse event with a true incidence rate from 1%–5% as shown in [Table 3](#).

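### SAP 4.3.1.6 counts antibiotic use for any cause under the name of an endpoint defined as antibiotic use for influenza-related complications

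*SAP*

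**What the plan says.** The endpoint in SAP Table 1 is "Proportion of participants requiring antibiotics for influenza related complications". The protocol synopsis, protocol Table 3 and the heading of SAP 4.3.1.6 word it the same way. The single sentence under that heading reads: "The number and percentage of patients requiring antibiotics for any reason will be presented by treatment group".

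SAP section 1 states: "There are no changes to the planned analyses described in the protocol". It also says that the SAP's analyses "will supersede those specified in Protocol YV44465 for the purposes of a regulatory filing".

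Three further provisions bear on the point:

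- SAP 4.3.1.5 identifies influenza-related complications from an item on the AE form: "If this event is one of the following influenza-related complications, select from the list".
- Protocol 6.8 has every concomitant medication recorded on its own eCRF page. The required fields include "Reason for use".
- Protocol 6.8.4 prohibits antibiotics from consent to the Day 15 assessments, with this exception: "Unless bacterial or fungal infection is suspected after study drug administration".

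Efficacy endpoints are analysed on the FASi (SAP 4.1), that is, dosed participants with PCR-confirmed influenza.

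**The concern.** The definition is cause-specific and the counting rule is all-cause. A programmer who follows 4.3.1.6 will put a child treated for an unrelated infection in the same row as a child treated for pneumonia or otitis media, and the table will carry the cause-specific title. Readers would take the percentage as a measure of complication-driven antibiotic use, which it may exceed.

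The change is also undeclared. If the all-cause count is deliberate, the statement in SAP section 1 that nothing has changed is wrong. If it is a drafting slip, the slip sits in the document that governs the filing.

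**Working it through.** **1. Definition against rule.**

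| Place | Which antibiotic use counts |
|---|---|
| Protocol synopsis and Table 3 | for influenza-related complications |
| SAP Table 1 | for influenza-related complications |
| SAP 4.3.1.6, heading | for influenza-related complications |
| SAP 4.3.1.6, analysis sentence | any cause |

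**2. Is the restricted count specified elsewhere?** SAP 4.3.1 points back to Table 1 for the definition but adds no counting rule. SAP 4.3.1.5 counts complications, not antibiotics. SAP 4.5.2 summarises concomitant treatment on the FAS without reference to complications. So the SAP has no rule for the endpoint as defined.

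**3. Can the two counts differ?** Yes.

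- The exception in protocol 6.8.4 covers any suspected bacterial or fungal infection after dosing, with no link to influenza.
- The prohibition ends at Day 15, but concomitant therapy is recorded to the completion or discontinuation visit (protocol 6.8). SAP 4.1.1 takes in all such data up to that date.
- SAP 4.3.1.6 sets no start point. Recording reaches back 2 weeks before study drug, whereas 4.3.1.5 limits complications to those after treatment.

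**4. Size per child.** The plan states no figure for this endpoint. Its only design figure, the 87% chance of seeing at least one event of 3% incidence in 67 participants, reproduces as 1 − 0.97^67 = 87.0%. It does not bear on this point.

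For one arm let n be the FASi size, c the children with at least one complication-driven antibiotic course, and u the children with antibiotics only for other reasons.

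- Defined endpoint: c/n
- SAP count: (c + u)/n
- Excess: u/n, which is zero only if u = 0

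Planned enrolment is "67 participants in the baloxavir marboxil treatment group and 33 participants in the oseltamivir treatment group". The FASi is a subset of those randomised, so at planned enrolment n is at most 67 and 33. Each such child then adds at least 1/67 = 1.5 percentage points or 1/33 = 3.0 percentage points.

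**5. Effect on the contrast between arms (assumed rates only).** Suppose complication-driven use is 3% against 9%, and unrelated use is q in both arms, independent of it. The any-cause proportion is 1 − (1 − p)(1 − q).

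| q | Proportions | Ratio | Difference |
|---|---|---|---|
| 0% | 3.0% vs 9.0% | 0.33 | 6.0 points |
| 5% | 7.9% vs 13.6% | 0.58 | 5.7 points |
| 10% | 12.7% vs 18.1% | 0.70 | 5.4 points |
| 20% | 22.4% vs 27.2% | 0.82 | 4.8 points |

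Under these assumptions the ratio moves toward 1 while the difference shrinks little. None of these rates is in the documents.

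**The case against.** **Little rests on it.** The primary objective is safety, all analyses are descriptive, and no hypothesis or sample size depends on this endpoint. The any-cause count contains every child who meets the definition. The reason for use is collected in any case, so the restricted row can still be produced before reporting. This stands, and it limits the severity.

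**An any-cause count has a merit.** The trial is open-label, so the site records the reason for an antibiotic knowing the arm. Counting all courses avoids that attribution. This also stands, but it argues for showing the any-cause count under its own label. It does not justify giving it the cause-specific title.

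**Unrelated use may be rare.** The exclusion criteria remove children whose infection needs a systemic antibiotic at screening, and protocol 6.8.4 limits use to Day 15. If unrelated use is close to nil, the two counts nearly coincide. That is possible, but neither provision guarantees it.

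**The restricted count needs work.** Complications are flagged on the AE form and reasons on the concomitant medication form, and the documents describe no link between them. The complication list includes death and hospitalization, which are not reasons to prescribe an antibiotic. This stands too: pointing to the 4.3.1.5 list is not enough, and a matching rule is needed.

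**Conclusion.** The mismatch is plain on the page and should be fixed. As written, the SAP gives no rule for the endpoint that it defines and would report a broader count under that name. The consequence is limited to the labelling and size of one descriptive secondary result. The minimum step per child holds at planned enrolment; it would be smaller if enrolment were increased and larger where the FASi falls short of the number randomised.

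A reader might infer three stronger things that the documents do not support:

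- **That the endpoint has been dropped.** It has not. Table 1 and the section heading keep it, and the data that it needs appear to be collected. The fault is a contradiction between definition and rule.
- **That the reported figure will be some multiple of the true one.** Any such multiple needs a rate of complication-driven use and a rate of unrelated use, and the documents give neither.
- **That the comparison between arms will be diluted.** That depends on the unrelated rates in each arm and on a real difference to dilute. Both are unknown, and 4.3.1.6 plans only counts and percentages by group.

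**What to change.** Replace the sentence in SAP 4.3.1.6 with a count of FASi participants who have at least one antibiotic started after first dose whose recorded reason for use corresponds to an influenza-related complication flagged on the AE form, as in 4.3.1.5. State the matching rule in the SAP. It should say how non-specific reasons, such as a suspected bacterial infection, are classified, and how flagged events that are outcomes rather than diagnoses (death, hospitalization) are treated. Apply the rule without reference to treatment arm, before any tables by arm are run.

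Keep the any-cause count as a separately labelled supplementary row. Arm-blind matching cannot undo a reason that the site recorded knowing the arm, and the any-cause row is the check on that. If the sponsor prefers the any-cause count as the endpoint, it should retitle the endpoint and declare the change in SAP section 1.

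The cost is a short SAP amendment and a manual review of the recorded reasons for antibiotic courses among roughly 100 children. No new data collection appears to be needed.
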